16.0 Statistical Considerations and Methodology

16.1 Overview

This is a phase II study of a novel regimen of ixazomib in combination with pomalidomide and dexamethasone for treatment of patients who are being considered for single ASCT for relapsed or refractory multiple myeloma. The study is designed to assess the progression-free survival at 18 months (PFS18) using a one-stage binomial study design.

16.11 Primary Endpoint

The primary endpoint of this trial is the proportion of patients alive and free from disease progression at 18 months from study entry. All patients meeting the eligibility criteria, who have signed a consent form and have begun treatment, will be evaluable for progression-free survival at 18 months (PFS18), unless they are determined to be a major violation.

16.2 Statistical Design:

16.21 Decision Rule

In a previous study including 112 patients who received a delayed autologous transplant after IMiD-based initial therapy, median progression-free survival from the time of transplant was 15.9 months (Kumar S 2012). In two additional studies with 64 patients and 65 patients who received novel agents during the pre-ASCT induction, the median progression-free survival from time of transplant was 22.2 months and 18 months, respectively, in patients who received a delayed transplant (Dunavin NC, 2013; Remenyi P, 2016).

Patients on the proposed study will also be undergoing delayed autologous transplantation; however, progression-free survival will be measured from study entry. Based on previous studies, a PFS18 rate from time of study entry of 50% would not be of interest.

The largest success proportion where the proposed treatment regimen would be considered ineffective in this population is 50%, and the smallest success proportion that would warrant subsequent studies with the proposed regimen in this patient population is 75%. The following one-stage binomial design uses 21 evaluable patients to test the null hypothesis that the true success proportion in a given patient population is at most 50%.

16.212 Final Decision Rule: If 13 or fewer successes are observed in the first 21 evaluable patients, we will consider this regimen ineffective in this patient population and terminate this study. Otherwise, if the number of successes is at least 14, this will be considered evidence of promising activity and the treatment may be recommended for further testing in subsequent studies in this population.

16.213 Over Accrual: If more than the target number of patients are accrued, the additional patients will not be used to evaluate the stopping rule or used in any decision making process. Analyses involving over accrued patients are discussed in Section 16.313.

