after primary therapy and proposed guidelines for the use of salvage HCT in MM. (Giralt et al, 2015). The expert committee recommended that salvage ASCT should be considered standard in transplantation-eligible patients relapsing after non SCT-based primary therapy and that the role of post salvage ASCT maintenance needs to be explored in the context of well-designed prospective trials that should include new agents, such as monoclonal antibodies, immune-modulating agents, and oral proteasome inhibitors (Giralt et al, 2015). Reinduction treatment with combination chemotherapy is the standard and most experts agree that high-dose therapy consolidation should be considered the standard of care at this time for this patient population. The experts agreed that this patient population of relapsed/refractory myeloma, although heterogeneous, is worthy of prospective trials designed to address the issue of optimal reinduction therapy and consolidation to determine whether their natural history is different than that for patients relapsing after a prior autograft. (Giralt et al. 2015).

The Mayo Clinic Group retrospectively studied 290 patients with untreated MM who received IMiD-based initial therapy (Kumar S et al., 2012) Patients who underwent a stem cell harvest attempt were considered transplantation-eligible and were included. SCT within 12 months of diagnosis and within 2 months of harvest were considered early SCT (n=173). SCT >12 months after diagnosis was considered delayed SCT (n=112). In the delayed SCT group, 42 patients had undergone SCT, and the median estimated time to SCT was 5.3 months and 44.5 months in the early SCT and delayed SCT groups, respectively. The 4-year overall survival rate from diagnosis was 73% in both groups. The time to progression after SCT was similar between the early and delayed SCT groups. These results indicated that, in transplantation-eligible patients who receive IMiDs as initial therapy followed by early stem cell mobilization, delayed SCT results in similar overall survival compared with early SCT (Kumar S et al., 2012).

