- 6.4 Prior to accepting the registration, registration/randomization application will verify the following:

- IRB approval at the registering institution
- Patient eligibility
- Existence of a signed consent form
- Existence of a signed authorization for use and disclosure of protected health information

- 6.5 Treatment on this protocol must commence at the recruiting institution under the supervision of a hematologist.

- 6.6 Treatment cannot begin prior to registration and must begin ≤ 14 days after registration.
- 6.7 Pretreatment tests/procedures (see Section 4.0) must be completed within the guidelines specified on the test schedule.
- 6.8 All required baseline symptoms (see Section 10.6) must be documented and graded.
- 6.9 Study drug is available on site.

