7.0 Protocol Treatment

7.1 Cycle lengths:

Cycles 1-3 = 28 days
 Cycle 4 = up to 56 days
 Cycle 5 = up to 120 days
 Cycles 6-8 = 28 days
 Cycle 9 = up to 56 days
 Cycles 10 and beyond = 28 days

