8.11 Instruction for initiation of a new cycle of therapy

A new cycle of treatment may begin on the scheduled Day 1 of a new cycle if:

- The ANC is $\geq 1.0 \times 10^9/L$ (=1000/microliter)
- The platelet count is $\geq 75 \times 10^9/L$ unless the participant has $\geq 50\%$ bone marrow infiltration in which case a platelet count of $\geq 50 \times 10^9/L$ is allowed
- Any other non-hematologic treatment -related adverse event that may have occurred has resolved to \leq Grade 1 or baseline severity.

If these conditions are not met on Day 1 of a new cycle, the subject will be evaluated weekly and a new cycle of therapy will be held until the toxicity has resolved as described below

If any drug dosing was halted during the previous cycle and was restarted with a one-level dose reduction without requiring an interruption for the remainder of the cycle, then that reduced dose level will be initiated on Day 1 of the new cycle.

If any drug dosing was omitted for the remainder of the previous cycle or if the new cycle is held due to known hematologic toxicity newly encountered on the scheduled Day 1, then the new cycle will be started with a one-level dose reduction. If a new cycle of therapy cannot be restarted within 4 weeks of the scheduled Day 1 due to non-resolution of drug related toxicities, the patient will be removed from protocol therapy and will go to event monitoring.

→ → Use the NCI Common Terminology Criteria for Adverse Events (CTCAE) version 4.0* unless otherwise specified ← ←

8.2 Dose modifications for ixazomib based on adverse events during a cycle (for each cycle during induction and consolidation and maintenance)

CTCAE System/Organ/Class (SOC)	ADVERSE EVENT	AGENT[#]	ACTION^{**}
Blood and lymphatic system disorders	Febrile neutropenia If platelet count $<30 \times 10^9/L$ or ANC $<1.0 \times 10^9/L$ or ANC $>1.0 \times 10^9/L$ (up to LLN) with fever (temperature $>38.5^\circ C$)	Ixazomib	Days 2-15: Ixazomib dose should be omitted. Complete blood count (CBC) with differential should be followed weekly. If ANC is $\geq 1.0 \times 10^9/L$ and/or platelet counts $\geq 30 \times 10^9/L$, ixazomib may be reinitiated with 1 dose level reduction (see Table 8.1). The subsequent cycle will use the reduced dose
Nervous System Disorders	Peripheral motor neuropathy OR Peripheral sensory neuropathy Newly developed Grade 1 with pain or \geq Grade 2	Ixazomib	Reduce dose of ixazomib to the next lower dose level

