16.23 Accrual Rate and Study Duration

We anticipate accruing 2 patients per month to this study, and hence the enrollment period will be approximately 2 years. An individual patient is expected to complete induction, ASCT and consolidation phases within 15 months of enrollment, after which ixazomib maintenance phase will start in which the drug is given until progression or unacceptable toxicity. The minimum duration before results may be reported is expected to be approximately 3.5 years, or until the last patient accrued has been observed for at least 18 months.

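### Does the 50% null for PFS18 need changing because Section 16.21 supports it with medians counted from transplant, not from study entry?

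*Combined protocol and SAP*

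**What the plan says.** Section 16.21 starts from a study including "112 patients who received a delayed autologous transplant after IMiD-based initial therapy, median progression-free survival from the time of transplant was 15.9 months". It adds two further studies with medians of 22.2 and 18 months, also counted from transplant. It then notes that patients in this trial will also have a delayed transplant; "however, progression-free survival will be measured from study entry". The null follows directly: "Based on previous studies, a PFS18 rate from time of study entry of 50% would not be of interest". The alternative is 75%, and the rule asks for at least 14 successes among 21 evaluable patients. Section 16.24 gives a significance level of 0.095 and power of 0.870 at 75%.

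Section 16.11 counts every eligible, consented patient who begins treatment, apart from major violations, whether or not that patient reaches transplant.

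Section 1.2 describes the first study too. It gives 112 as the size of the delayed group and adds: "In the delayed SCT group, 42 patients had undergone SCT".

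**The concern.** In a single-arm trial the null is the only comparator, and here the supporting evidence and the endpoint use different clocks. Read at 18 months after transplant, the three medians give about 0.46, 0.50 and 0.57, so 50% looks as though it was read off the transplant clock and applied to another. If the historical rate from study entry were above 0.50, the chance of calling an uninteresting regimen promising would exceed the stated 0.095; if below, the rule would be stricter than it appears.

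The rule is also sensitive. With 21 patients, each 0.05 step in the null moves by one patient the cutoff that keeps the error just under 0.10. The 112-versus-42 discrepancy adds doubt about how firm the first benchmark is.

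**Working it through.** **1. The plan's own figures.** Exact binomial P(X ≥ 14 | n = 21, p) is 0.0946, 0.1971, 0.3495, 0.5365, 0.7230 and 0.8701 for p = 0.50, 0.55, 0.60, 0.65, 0.70 and 0.75. These match the table in Section 16.24 at its printed precision.

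**2. When transplant falls on the study-entry clock.** Section 6.6: "Treatment cannot begin prior to registration and must begin ≤ 14 days after registration". Induction is four 28-day cycles and Section 7.2 allows 2 to 4 weeks before transplant, which agrees with Section 7.1 ("Cycle 4 = up to 56 days"; 28 + 28 = 56).
- Earliest: 4 × 28 + 14 = 126 days.
- Latest without delays: 4 × 28 + 28 + 14 = 154 days.
- At 30.4375 days per month, month 18 is 18 − 126/30.4375 = 13.86 or 18 − 154/30.4375 = 12.94 months after transplant.

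**3. Conversion.** Assume exponential PFS after transplant, and let *a* be the share progressing or dying before it. Everyone else is treated as transplanted. Then S = (1 − a) × 0.5^(t/median), where t is months from transplant to month 18. The value of *a* that gives exactly 50% is 1 − 0.5/S₀, where S₀ is S at a = 0.

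| Median (months) | S₀, day 126 | S₀, day 154 | *a* giving 50% |
|---|---|---|---|
| 15.9 | 0.546 | 0.569 | 0.085 to 0.121 |
| 18 | 0.586 | 0.608 | 0.147 to 0.177 |
| 22.2 | 0.649 | 0.668 | 0.229 to 0.251 |

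**4. Range for assumed losses.** The documents give no value for *a*, so these are assumptions. Ranges cover both transplant days and all three medians.

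| Assumed *a* | Historical PFS18 from entry | P(≥14/21) at that rate |
|---|---|---|
| 10% | 0.492 to 0.601 | 0.083 to 0.353 |
| 15% | 0.465 to 0.567 | 0.050 to 0.245 |
| 20% | 0.437 to 0.534 | 0.029 to 0.159 |
| 25% | 0.410 to 0.501 | 0.016 to 0.096 |

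**5. Delays.** Section 8.11 removes a patient from protocol therapy "If a new cycle of therapy cannot be restarted within 4 weeks of the scheduled Day 1", so each hold can add up to 28 days. One hold puts transplant as late as day 182, two at day 210 and three at day 238. Even three fit the timeline in Section 16.23 ("An individual patient is expected to complete induction, ASCT and consolidation phases within 15 months of enrollment"): 238 + 60 days to consolidation + 4 × 28 = 410 days, against about 457 for 15 months. No single delayed day is therefore an upper limit. At *a* = 10% and median 22.2, PFS18 is 0.618, 0.636 and 0.655 for days 182, 210 and 238, with P(≥14/21) of 0.42, 0.48 and 0.56. Over days 126 to 182, Weibull shapes of 0.8 to 1.5 give break-even losses of 7% to 34%.

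**6. What other nulls would mean at n = 21.**

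| Null | Cutoff | Error | Power at 0.75 |
|---|---|---|---|
| 0.45 | 13 | 0.091 | 0.944 |
| 0.50 | 14 | 0.095 | 0.870 |
| 0.55 | 15 | 0.096 | 0.744 |
| 0.60 | 16 | 0.096 | 0.567 |

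A cutoff of 13 would pass a regimen with a true rate of 50% with probability 0.19.

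**7. 112 versus 42.** If every transplanted patient had an event (the best case), an approximate 95% range for the median is 15.9 × exp(±1.96/√events). That is 11.8 to 21.5 months with 42 events and 13.2 to 19.1 with 112. The centre does not move.

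**The case for a change.** The strongest case for a change is that Section 16.21 expressly rests the null on earlier studies, and acknowledging a different time origin is not converting for it. With little loss before transplant the converted rate sits above 0.50 for all three medians. At 10% loss and no delays, the chance of passing at the historical rate could reach 0.35. A few sentences stating the time to transplant and the assumed loss would make the null checkable.

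What stands is that the derivation is missing and the reader has to supply it. What does not follow is a different null:

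- The conversion gives three answers, not one. At day 126 and 10% loss they are 0.49, 0.53 and 0.58, and nothing in the documents says which median should govern.
- The deciding input, loss before transplant, is not in the documents. Writing in an assumed value would display a judgement without removing it.
- The populations differ in ways that a time shift cannot repair. Section 1.2 itself cautions against carrying the delayed-transplant results over to patients who have failed several lines, and Section 12.2 provides for patients with four or more prior therapies.
- Moving the cutoff has costs. Going to 15 lowers power at 0.75 from 0.870 to 0.744; going to 13 doubles the chance of passing a rate the plan calls uninteresting. In an open single-arm trial whose investigators and statistician review endpoint problems at least twice a year (Section 16.41), a change of cutoff during the trial could also be influenced by accumulating failures.

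**Conclusion.** The observation is accurate, but it does not call for a change. The 50% null is partly a judgement about what rate would be uninteresting. It lies inside the converted historical range at every assumed loss from 10% to 25%, and without delays it is the exact break-even at about 9% to 25% loss before transplant. Delays raise the converted rate and other curve shapes widen the break-even range, but neither identifies a better value. These figures rest on exponential curves after transplant, on the protocol's own schedule, and on loss shares that are assumptions.

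The decision itself is modest: 14 or more successes mean only that the regimen may be recommended for further testing. Section 16.312 also reports the proportion with an exact 95% interval, so a reader who prefers another benchmark can apply it. At 14/21 that interval runs from 0.43 to 0.85 (the 2.5% point of Beta(14, 8) and the 97.5% point of Beta(15, 7)), wide enough to cover nearly all the benchmark values in question.

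The 112-versus-42 discrepancy is a clerical slip: Section 16.21 repeats the size of the delayed group as though all of it had been transplanted. How many patients lie behind the 15.9-month median is not stated; 42 is an inference from Section 1.2. Either count leaves the null, the sample size and the 14/21 rule where they are.

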16.22 Sample Size

The one stage study design to be used is fully described above. A maximum of 21 evaluable patients will be accrued onto this phase II study unless undue toxicity is encountered. We anticipate accruing an additional 4 patients to account for ineligibility, cancellation, major treatment violation, or other reasons. Therefore, the total sample size will be 25 patients.

16.23 Accrual Rate and Study Duration

We anticipate accruing 2 patients per month to this study, and hence the enrollment period will be approximately 2 years. An individual patient is expected to complete induction, ASCT and consolidation phases within 15 months of enrollment, after which ixazomib maintenance phase will start in which the drug is given until progression or unacceptable toxicity. The minimum duration before results may be reported is expected to be approximately 3.5 years, or until the last patient accrued has been observed for at least 18 months.

16.24 Power and Significance Level

Assuming that the number of successes is binomially distributed, the significance level is 0.095. The probability of declaring that this regimen warrants further studies (i.e. statistical power) under various success proportions can be tabulated as a function of the true success proportion as shown in the following table.

If the true success proportion is...	0.50	0.55	0.60	0.65	0.70	0.75
Then the probability of declaring that the regimen warrants further study is...	0.095	0.197	0.350	0.537	0.723	0.870

16.25 Other considerations

Adverse events, quality/duration of response, and patterns of treatment failure observed in this study, as well as scientific discoveries or changes in standard care will be taken into account in any decision to terminate the study

16.3 Analysis Plan

The analysis for this trial will commence at planned time points (see 16.2) and at the time the patients have become evaluable for the primary endpoint. The Statistician and Study Chair will make the decision, in accord with CCS Standard Operating Procedures, availability of data for secondary endpoints (e.g., laboratory correlates), and the level of data maturity. It is anticipated that the earliest date in which the results will be made available via manuscript, abstract, or presentation format is when last patient has been followed for at least 18 months.

16.31 Primary Outcome Analyses:

16.311 Definition: The primary endpoint of this trial is the proportion of patients alive and free from disease progression at 18 months from study entry. All patients meeting the eligibility criteria, who have signed a consent form and have begun treatment, will be evaluable for progression-free survival at 18 months unless they are determined to be a major violation.
Definition of Success: An evaluable patient will be classified as a

treatment success for the primary endpoint if they are alive and free from disease progression at 18 months from registration.

- 16.312 Estimation: The proportion of successes will be estimated by the number of successes divided by the total number of evaluable patients. Exact binomial 95% confidence intervals for the true success proportion will be calculated. If patients are censored prior to 18 months post registration (which is unlikely given our data from past trials in a similar patient population), a Kaplan Meier (Kaplan, E. and Meier, P., 1958) estimate for PFS18 along with the 95% confidence intervals will be reported. We recognize that applying this approach will, however, reduce the stated statistical power of our primary analysis.
- 16.313 Over Accrual: If more than the target number of patients are accrued, the additional patients will not be used to evaluate the stopping rule or used in any decision making processes; however, they will be included in final point estimates and confidence intervals.

16.32 Secondary Outcome Analyses

- 16.321 The overall response rate will be estimated by the number of patients who achieve a sCR, CR, VGPR, or PR divided by the total number of evaluable patients. All evaluable patients will be used for this analysis. Exact binomial 95% confidence intervals for the true overall response rate will be calculated.
- 16.322 The \geq VGPR response rate will be estimated by the number of patients who achieve a sCR, CR, or VGPR divided by the total number of evaluable patients. All evaluable patients will be used for this analysis. Exact binomial 95% confidence intervals for the true overall \geq VGPR response rate will be calculated.
- 16.323 Overall survival is defined as the time from registration to the last date of documentation of follow-up or death due to any cause. The distribution of overall survival will be estimated using the method of Kaplan-Meier (Kaplan, E. and Meier, P., 1958)
- 16.322 Adverse Events: All eligible patients that have initiated treatment will be considered evaluable for assessing adverse event rate(s). The maximum grade for each type of adverse event will be recorded for each patient, and frequency tables will be reviewed to determine patterns. Additionally, the relationship of the adverse event(s) to the study treatment will be taken into consideration.

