13.6 Ineligible

A patient is deemed *ineligible* if after registration, it is determined that at the time of registration, the patient did not satisfy each and every eligibility criteria for study entry. The patient may continue treatment off-protocol at the discretion of the physician as long as there are no safety concerns, and the patient was properly registered. The patient will go directly to the event-monitoring phase of the study (or off study, if applicable).

- If the patient received treatment, all data up until the point of confirmation of ineligibility must be submitted. Event monitoring will be required per Section 18.0 of the protocol.
- If the patient never received treatment, on-study material and the End of Active Treatment/Cancel Notification Form must be submitted. No further data submission is necessary.

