16.42 Adverse Event Stopping Rules

The stopping rules specified below are based on the knowledge available at study development. We note that the Adverse Event Stopping Rule may be adjusted in the event of either (1) the study re-opening to accrual or (2) at any time during the conduct of the trial and in consideration of newly acquired information regarding the adverse event profile of the treatment(s) under investigation. The study team may choose to suspend accrual because of unexpected adverse event profiles that have not crossed the specified rule below.

Accrual will be temporarily suspended to this study if at any time we observe events considered at least possibly related to study treatment (i.e. an adverse event with attribute specified as “possible,” “probable,” or “definite”) that satisfy one of the following:

- if 3 or more patients in the first 10 treated patients experience a grade 4 or higher non-hematologic adverse event at least possibly related to treatment.
- if after the first 10 patients have been treated, 30% of all patients experience a grade 4 or higher non-hematologic adverse event at least possibly related to treatment.

We note that we will review grade 4 and 5 adverse events deemed “unrelated” or “unlikely to be related”, to verify their attribution and to monitor the emergence of a previously unrecognized treatment-related adverse event.

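### Adverse-event rates leave out treated patients later found ineligible, so they need not describe everyone exposed; the error can run in either direction

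*Combined protocol and SAP*

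**What the plan says.** The Adverse Events item of Section 16.32 (the second item numbered 16.322) sets two conditions for the adverse-event set, eligibility and having started treatment: "All eligible patients that have initiated treatment will be considered evaluable for assessing adverse event rate(s").

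Section 13.6 makes ineligibility a finding reached after registration, when "it is determined that at the time of registration, the patient did not satisfy each and every eligibility criteria for study entry". It expects some of these patients to have been dosed already: "If the patient received treatment, all data up until the point of confirmation of ineligibility must be submitted". They then move to event monitoring and may continue treatment off-protocol.

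The stopping rule in Section 16.42 carries no eligibility condition. Its first clause acts "if 3 or more patients in the first 10 treated patients experience a grade 4 or higher non-hematologic adverse event"; only events with a possible or stronger link to therapy count. Its second clause, once 10 patients have been treated, acts if "30% of all patients experience a grade 4 or higher non-hematologic adverse event at least possibly related to treatment".

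Section 16.22 allows for losses: "We anticipate accruing an additional 4 patients to account for ineligibility, cancellation, major treatment violation, or other reasons". It continues: "Therefore, the total sample size will be 25 patients".

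**The concern.** Adverse-event rates are normally meant to describe what happened to the people who took the drug. A patient dosed and later found ineligible was exposed all the same, and Section 13.6 already requires the data. An eligibility filter can be argued for the efficacy endpoint in Section 16.11; it has no comparable rationale for describing harm.

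The exclusion need not be neutral. Several criteria in Sections 3.1 and 3.2 concern organ function, blood counts, neuropathy, QTc and unresolved toxicity. Section 1.3 reports unbound ixazomib exposure 38% higher in severe renal impairment or dialysis-dependent disease, and 27% higher in moderate or severe hepatic impairment. A patient enrolled in error on such grounds could plausibly be at different risk from the rest.

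At stake are the accuracy of the published rates and their agreement with the stopping-rule count. If an affected patient who helped trigger a suspension of accrual is later found ineligible, the final table will not show that count. Section 16.25 also says adverse events are weighed in any decision to end the study.

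**Working it through.** **The plan's own figures.** The plan gives no number for the adverse-event set. Its design figures serve only to show what does not change. With 21 evaluable patients and success at 14 or more, the exact binomial tail is P(X ≥ 14) = 0.0946 at p = 0.50 and 0.8701 at p = 0.75. Section 16.24 states 0.095 and 0.870. The adverse-event set does not enter this calculation.

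**Who is left out of which set.**
- Cancelled patients (Section 13.8) were never treated and belong in no adverse-event set.
- Major violations (Section 13.7) are removed from the primary endpoint set (Sections 16.11 and 16.311), but Section 16.32 does not remove them from the adverse-event set.
- Patients treated and then found ineligible are the only exposed group that Section 16.32 drops.

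The allowance of 4 covers all of these and other reasons too. So 4/25 = 16% is a ceiling for the dropped group, not an estimate.

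**Effect of one exclusion.** Let N patients be treated, x of them with the event.
- Dropping an affected patient lowers the rate by x/N − (x−1)/(N−1) = (N−x)/[N(N−1)].
- Dropping an unaffected patient raises it by x/(N−1) − x/N = x/[N(N−1)].

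Assume N = 25 and x = 3, where 3/25 = 12.0%:
- Affected patient dropped: 2/24 = 8.3%, a fall of 22/600 = 3.7 points.
- Unaffected patient dropped: 3/24 = 12.5%, a rise of 3/600 = 0.5 points.

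For 1 ≤ x ≤ 24 the largest change either way is 24/600 = 4.0 points.

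**Several exclusions.** Assume all 25 are treated, k are later found ineligible, and 5 of the eligible patients have the event. The last column runs from none to all of the k having it.

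| k | Rate as written | Rate in all 25 treated |
|---|---|---|
| 1 | 5/24 = 20.8% | 5/25 to 6/25 = 20% to 24% |
| 2 | 5/23 = 21.7% | 5/25 to 7/25 = 20% to 28% |
| 4 | 5/21 = 23.8% | 5/25 to 9/25 = 20% to 36% |

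**Agreement with the stopping rule.** Consider only the events the rule counts, and assume one affected patient is later found ineligible.
- 3/10 treated (30%) triggers the first clause; the analysis set shows 2/9 = 22.2%.
- 8/25 (32%) exceeds the 30% in the second clause, taking its denominator as all 25 treated; the analysis set shows 7/24 = 29.2%.

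**The case against.** The strongest reply is that this is one descriptive table. No eligibility restriction appears in the stopping rule (16.42), expedited reporting (10.4), death reporting (10.52), routine submission of adverse events (10.62), reporting to the manufacturer (10.8) or the twice-yearly monitoring board review (16.41). Toxicity in an ineligible patient still reaches those who protect participants. A running trigger and a final summary may reasonably use different sets, and no decision rule uses the 16.32 rate. Section 6.4 has eligibility verified before registration is accepted, which makes the case less likely. All of this stands, and it limits the point to the 16.32 rates and tables.

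Four stronger readings are tempting, and the documents support none of them.
- *The plan understates toxicity.* The direction depends on whether the excluded patients had events. Eligibility failures can also be matters of test timing, with no bearing on risk.
- *Sixteen percent of patients are dropped.* The allowance also covers never-treated cancellations, and major violations that stay in the adverse-event set.
- *Major violations are lost from safety too.* Section 16.32 does not exclude them.
- *The change has no downside.* Section 13.6 requires full data only until ineligibility is confirmed. The added patients may therefore be observed for less time, which can itself pull a maximum-grade rate down.

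None of this supplies a reason for keeping the eligibility condition.

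**Conclusion.** The point holds in a limited form. As written, Section 16.32 omits any treated patient later found ineligible from the adverse-event rates, although data on that patient are collected, and it uses a different set from Section 16.42. The consequence is a rate that may not describe all exposed patients, with unknown direction and size. One exclusion from 25 treated shifts a rate by at most 4 points. The number of exclusions is not given and could reach 4 only if the entire allowance were of this one kind. If no treated patient is found ineligible, there is no effect.

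The worked rates rest on assumed event counts and on all 25 registered patients being treated. A reader might infer that safety oversight is weakened or that the stopping rule contradicts itself; neither follows, because the rule and the reporting requirements apply regardless of eligibility. Alpha, power, the 14-of-21 rule and the sample size are untouched. This is a cheap improvement.

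**What to change.** In the Adverse Events item of Section 16.32, delete the word *eligible* and define the set explicitly: every patient who received at least one dose of any study drug is evaluable for adverse events, whatever is later found about eligibility. In the adverse-event tables, mark each patient whose data end when ineligibility was confirmed, so that the shorter observation is visible.

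The cost is a small edit and a footnote. The data needed up to confirmation are already required by Section 13.6, and no additional patients are needed. The one drawback is the shorter observation in the added patients, which the footnote discloses.
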